11.3 Reporting Requirements

For multi-site trials where a DF/HCC investigator is serving as the principal investigator, each participating investigator is required to abide by the reporting requirements set by the DF/HCC. The study must be conducted in compliance with FDA regulations, local safety reporting requirements, and reporting requirements of the principal investigator.

Each investigative site will be responsible to report SAEs that occur at that institution to their respective IRB. It is the responsibility of each participating investigator to report serious adverse events to the study sponsor and/or others as described below.

11.4 Reporting to the Study Sponsor

11.4.1 Serious Adverse Event Reporting

All serious adverse events that occur after the initial dose of study treatment, during treatment, or within 30 days of the last dose of treatment must be reported to the DF/HCC Overall Principal Investigator on the local institutional SAE form. This includes events meeting the criteria outlined in Section 11.1.2, as well as the following:

- Grade 2 (moderate) and Grade 3 (severe) events that are unexpected and at least possibly related/associated with the intervention.
- All Grade 4 (life-threatening or disabling) events that are unexpected or not specifically listed in the protocol as not requiring reporting.
- All Grade 5 (fatal) events while the participant is enrolled and actively participating in the trial OR when the event occurs within 30 days of the last study intervention.

Note: If the participant is in long term follow up, report the death at the time of continuing review.

Participating investigators must report each serious adverse event to the DF/HCC Overall Principal Investigator within 1 business day of learning of the occurrence. In the event that the participating investigator does not become aware of the serious adverse event immediately (e.g., participant sought treatment elsewhere), the participating investigator is to report the event within 1 business day after learning of it and document the time of

his or her first awareness of the adverse event. Report serious adverse events by facsimile (preferred), email, or telephone to:

[name] [contact] **[contact]** [contact] Email: [contact]

Within the following 24-48 hours, the participating investigator must provide follow-up information on the serious adverse event. Follow-up information should describe whether the event has resolved or continues, if and how the event was treated, and whether the participant will continue or discontinue study participation.

For multi-institution studies where a DF/HCC investigator is serving as the Overall Principal Investigator, each participating institution must abide by the reporting requirements set by the DF/HCC. This applies to any medical event equivalent to an unexpected grade 2 or 3 with a possible, probable or definite attribution, unexpected grade 4 toxicities, and grade 5 (death) regardless of study phase or attribution.

11.4.2 Non-Serious Adverse Event Reporting

Non-serious adverse events will be reported to the DF/HCC Overall Principal Investigator on the toxicity Case Report Forms.

81 CONFIDENTIAL

The Investigator should include his or her assessment of the causal relationship between each SAE and the Grantor product in the form faxed to Grantor and NCCN.

11.6 Reporting to the Institutional Review Board (IRB)

Investigative sites within DF/HCC will report all serious adverse events directly to the DFCI Office for Human Research Studies (OHRS).

Other investigative at external sites will report SAEs to their respective IRB according to the local IRB's policies and procedures in reporting adverse events. A copy of the submitted institutional SAE form should be forwarded to the Overall PI within the timeframes detailed in the table below.

DF/HCC Reportable AEs							
Attribution	AttributionGr. 2 & 3 AE ExpectedGr. 2 & 3 AE UnexpectedGr. 4 AE ExpectedGr. 4 AE UnexpectedGr. 5 AE Expected						
Unrelated Unlikely	Not required	Not required	5 calendar days [#]	5 calendar days	24 hours*		
Possible Probable Definite	Not required	5 calendar days	5 calendar days [#]	5 calendar days	24 hours*		
# If listed in protocol as expected and not requiring expedited reporting, event does not need to be reported.							
* For participants enrolled and actively participating in the study or for AEs occurring within 30 days of the last intervention, the AE should be reported within 24 business hours of learning of the event.							

Other investigators must submit SAE reports to the Overall PI via this contact information:

[name] [contact] **[contact]** [contact] Email: [contact]

The Overall PI will submit SAE reports from outside institutions to the DFCI OHRS according to DFCI IRB policies and procedures in reporting adverse events.

11.7 Reporting to the Food and Drug Administration (FDA)

The DF/HCC Overall Principal Investigator, as holder of the IND, will be responsible for all communication with the FDA. The DF/HCC Overall Principal Investigator will report to the FDA, regardless of the site of occurrence, any adverse event that is serious, unexpected and reasonably related (i.e., possible, probable, definite) to the investigational agents.

Unexpected fatal or life-threatening experiences associated with the use of the investigational agents will be reported to FDA as soon as possible but in no event later than 7 calendar days after initial receipt of the information.

All other serious unexpected experiences associated with the use of the investigational agents will be reported to FDA as soon as possible but in no event later than 15 calendar days after initial receipt of the information.

Events will be reported to the FDA using Form FDA 3500A (Mandatory Reporting Form for investigational agents) by sending the paper report via overnight, traceable delivery service. Forms are available at http://www.fda.gov/medwatch/getforms.htm

11.8 Reporting to Hospital Risk Management

Participating investigators will report to their local Risk Management office any subject safety reports or sentinel events that require reporting according to institutional policy.

11.9 Monitoring of Adverse Events and Period of Observation

All adverse events, both serious and non-serious, and deaths that are encountered from initiation of study intervention, throughout the study, and within 30 days of the last study intervention should be followed to their resolution, or until the participating investigator assesses them as stable, or the participating investigator determines the event to be irreversible, or the participant is lost to follow-up. The presence and resolution of AEs and SAEs (with dates) should be documented on the appropriate case report form and recorded in the participant's medical record to facilitate source data verification.

For some SAEs, the study sponsor or designee may follow-up by telephone, fax, and/or monitoring visit to obtain additional case details deemed necessary to appropriately evaluate the SAE report (e.g., hospital discharge summary, consultant report, or autopsy report).

Participants should be instructed to report any serious post-study event(s) that might reasonably be related to participation in this study. Participating investigators should notify the DF/HCC Overall Principal Investigator and their respective IRB of any unanticipated death or adverse event occurring after a participant has discontinued or terminated study participation that may reasonably be related to the study.

12. DATA AND SAFETY MONITORING

12.1 Data Reporting

12.1.1 Method

The QACT will collect, manage, and monitor data for this study.

12.1.2 Data Submission

The schedule for completion and submission of case report forms (paper or electronic) to the QACT is as follows:

Form	Submission Timeline
Eligibility Checklist	Complete prior to registration with QACT
On Study Form	Within 14 days of registration
Baseline Assessment Form	Within 14 days of registration
Treatment Form	Within 10 days of the last day of the cycle
Adverse Event Report Form	Within 10 days of the last day of the cycle
Response Assessment Form	Within 10 days of the completion of the cycle required for response evaluation
Off Treatment/Off Study Form	Within 14 days of completing treatment or being taken off study for any reason
Follow up/Survival Form	Within 14 days of the protocol defined follow up visit date or call

12.2 Safety Meetings

The DF/HCC Data and Safety Monitoring Committee (DSMC) will review and monitor toxicity and accrual data from this trial. The committee is composed of clinical specialists with experience in oncology and who have no direct relationship with the study. Information that raises any questions about participant safety will be addressed with the Principal Investigator and study team.

The DSMC will meet quarterly and/or more often if required to review toxicity and accrual data. Information to be provided to the committee may include: up-to-date participant accrual; current dose level information; DLT information; all grade 2 or higher unexpected adverse events that have been reported; summary of all deaths occurring within 30 days for Phase I or II protocols; for gene transfer protocols, summary of all deaths while being treated and during active follow-up; any response information;

audit results, and a summary provided by the study team. Other information (e.g. scans, laboratory values) will be provided upon request.

12.3 Monitoring

Involvement in this study as a participating investigator implies acceptance of potential audits or inspections, including source data verification, by representatives designated by the DF/HCC Overall Principal Investigator (or Protocol Chair) or DF/HCC. The purpose of these audits or inspections is to examine study-related activities and documents to determine whether these activities were conducted and data were recorded, analyzed, and accurately reported in accordance with the protocol, institutional policy, and any applicable regulatory requirements.

All data will be monitored for timeliness of submission, completeness, and adherence to protocol requirements. Monitoring will begin at the time of participant registration and will continue during protocol performance and completion. Please see Section 5.0 of the Data and Safety Monitoring Plan (Appendix C) for monitoring details.

13. REGULATORY CONSIDERATIONS

13.1 Protocol Review and Amendments

This protocol, the proposed informed consent and all forms of participant information related to the study (e.g., advertisements used to recruit participants) and any other necessary documents must be submitted, reviewed and approved by a properly constituted IRB governing each study location.

Any changes made to the protocol must be submitted as amendments and must be approved by the IRB prior to implementation. Any changes in study conduct must be reported to the IRB. The DF/HCC Overall Principal Investigator (or Protocol Chair) will disseminate protocol amendment information to all participating investigators.

All decisions of the IRB concerning the conduct of the study must be made in writing.

13.2 Informed Consent

All participants must be provided a consent form describing this study and providing sufficient information for participants to make an informed decision about their participation in this study. The formal consent of a participant, using the IRB approved consent form, must be obtained before the participant is involved in any study-related procedure. The consent form must be signed and dated by the participant or the participant's legally authorized representative, and by the person obtaining the consent. The participant must be given a copy of the signed and dated consent document. The original signed copy of the consent document must be retained in the medical record or research file.

13.3 Ethics

This study is to be conducted according to the following considerations, which represent good and sound research practice:

- US Code of Federal Regulations (CFR) governing clinical study conduct and ethical principles that have their origin in the Declaration of Helsinki
 - Title 21 Part 50 Protection of Human Subjects www.access.gpo.gov/nara/cfr/waisidx_02/21cfr50_02.html
 - Title 21 Part 54 Financial Disclosure by Clinical Investigators www.access.gpo.gov/nara/cfr/waisidx_02/21cfr54_02.html
 - Title 21 Part 56 Institutional Review Boards www.access.gpo.gov/nara/cfr/waisidx_02/21cfr56_02.html
 - Title 21 Part 312 Investigational New Drug Application www.access.gpo.gov/nara/cfr/waisidx_02/21cfr312_02.html
- State laws
- DF/HCC research policies and procedures http://www.dfhcc.harvard.edu/clinical-research-support/clinical-research-unit-cru/policies-and-procedures/

It is understood that deviations from the protocol should be avoided, except when necessary to eliminate an immediate hazard to a research participant. In such case, the deviation must be reported to the IRB according to the local reporting policy.

13.4 Study Documentation

The investigator must prepare and maintain adequate and accurate case histories designed to record all observations and other data pertinent to the study for each research participant. This information enables the study to be fully documented and the study data to be subsequently verified.

Original source documents supporting entries in the case report forms include but are not limited to hospital records, clinical charts, laboratory and pharmacy records, recorded data from automated instruments, microfiches, photographic negatives, microfilm or magnetic media, and/or x-rays.

13.5 Records Retention

All study-related documents must be retained for the maximum period required by applicable federal regulations and guidelines or institutional policies.

13.6 Multi-center Guidelines

This protocol will adhere to the policies and requirements of the Dana-Farber/Harvard Cancer Center. The specific responsibilities of the DF/HCC Overall Principal Investigator (or Protocol Chair), Coordinating Center, and Participating Institutions are presented in the Dana-Farber/Harvard Cancer Center Multi-Center Data and Safety Monitoring Plan (see Appendix C)

- The DF/HCC Overall Principal Investigator/Coordinating Center is responsible for distributing all IND Action Letters or Safety Reports to all participating institutions for submission to their individual IRBs for action as required.
- Mechanisms will be in place to ensure quality assurance, protocol compliance, and adverse event reporting at each site.
- Except in very unusual circumstances, each participating institution will order the agents directly from the supplier. A participating site may order the agents only after the initial IRB approval for the site has been forwarded to the Coordinating Center.

14. STATISTICAL CONSIDERATIONS

14.1 Study Design/Endpoints

14.1.1 Study Design

This is an open label single-arm single-stage phase II multicenter trial.

14.1.2 Primary Objective

To assess the activity of GSK1120212 and GSK2141795 in combination in patients with recurrent or persistent cervical cancer. Activity will be ascertained by estimation of best objective tumor response per RECIST version 1.1.

14.1.3 Secondary Objectives

- To assess the duration of progression-free and overall survival following initiation of therapy with GSK1120212 and GSK2141795
- To determine the nature and degree of toxicity of GSK1120212 and GSK2141795 as assessed by version 4 of the NCI Common Terminology Criteria for Adverse Events (CTCAE) in this cohort of patients.
- To describe the mutation and co-mutation rates of genes in the PI3K and RAS-ERK signaling pathways in recurrent cervical cancer using high throughput targeted mutational analysis on participant tumor samples.
- To explore the association of mutational status with clinical benefit from GSK1120212 and GSK2141795.

14.2 Statistical Analysis

The primary objective of this study is estimation of the best objective response rate (CR + PR) per RECIST 1.1. With the planned accrual of 35 participants to this single-arm trial, there is 91% power to detect an improvement in response rate from 0.07 to 0.22 using a one-sided 0.09-level exact binomial test. Therefore, the null hypothesis will be rejected if 5 or more participants respond to combination therapy with GSK1120212 and GSK2141795. The null hypothesis of 0.07 is based on a weighted average of the observed response rates from the 11 cohorts enrolled to GOG 127 and 227 series.

Secondary objectives include progression-free and overall survival, both of which will be estimated by the Kaplan-Meier method. PFS is defined as the time from registration to the study until documented disease progression or death without progression, whichever occurs first. Participants not experiencing a PFS event will be censored at the last date of documented disease evaluation. Overall survival is defined as the time from study registration to the time of death from any cause, with follow-up censored at the last date

known to be alive. Cox's proportional hazards models will be fitted to explore significant predictors of event-time endpoints.

Toxicity data will be tabulated and compared between any groups of interest using Fisher's exact tests, and will be routinely monitored, analyzed and reviewed by the DF/HCC DSMC.

Molecular correlative analyses will be conducted and all patient outcomes: response, PFS, OS and toxicity will be compared between the PIK3CA and RAS-isoform mutated and WT groups using the statistical methodologies specified above; estimating the proportion of participants harboring mutations in both genes is also of interest, as is comparing their outcomes to those in the remainder of the cohort. These analyses are considered exploratory and will not be adjusted for multiple comparisons.

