14.3 Sample Size/Accrual Rate

The planned sample size is a maximum of 35 participants. The estimated monthly accrual rate is 2 participants. Participants will be followed for a maximum of 3 years.

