14.4.2 Evaluation of Response

All participants included in the study must be assessed for response to treatment, even if there are major protocol treatment deviations or if they are ineligible. Each participant should be assigned one of the following categories: 1) complete response, 2) partial response, 3) stable disease, 4) progressive disease, 5) early death from malignant disease, 6) early death from toxicity, 7) early death because of other cause, or 9) unknown (not assessable, insufficient data). By arbitrary convention, category 9 usually designates the "unknown" status of any type of data in a clinical database.

All participants who have measurable disease present at baseline, have received at least one cycle of therapy, and have had their disease re-evaluated will be considered evaluable for response. Participants in response categories 5-9 will not be considered evaluable but will remain within the intention to treat analysis.

Participants who develop brain metastasis on study, but continue on study after definitive treatment of their cranial disease, will be considered to have had progressive disease at the point of the diagnosis of the initial brain metastasis.

All conclusions should be based on all evaluable participants. Subanalyses may then be performed on the basis of a subset of participants, excluding those for whom major protocol deviations have been identified (e.g., early death due to other reasons, early discontinuation of treatment, major protocol violations, etc.). However, these subanalyses may not serve as the basis for drawing conclusions concerning treatment efficacy, and the

reasons for excluding participants from the analysis should be clearly reported. The 95% confidence intervals should also be provided.

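### Is the primary test mislabelled as 0.09-level when its exact one-sided type I error is 0.0948?

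*Combined protocol and SAP*

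**What the plan says.** Section 14.1.1 describes the design: "This is an open label single-arm single-stage phase II multicenter trial". There is no interim look that would alter the error rates.

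Section 14.2 sets out the primary test. It starts from the accrual target ("With the planned accrual of 35 participants to this single-arm trial") and states that "there is 91% power to detect an improvement in response rate from 0.07 to 0.22 using a one-sided 0.09-level exact binomial test". The decision rule follows as a responder count: "Therefore, the null hypothesis will be rejected if 5 or more participants respond to combination therapy". The null rate is explained by its source: "The null hypothesis of 0.07 is based on a weighted average of the observed response rates from the 11 cohorts" of two earlier trial series.

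Section 14.3 repeats the sample size: "The planned sample size is a maximum of 35 participants".

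The response rates and the level are printed to two decimals and the power as a whole percentage.

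**The concern.** An exact binomial test can attain only certain type I error rates, because the number of responders is a whole number. In strict usage, the level of a test is an upper bound on its size. With 35 participants and a null rate of 0.07, rejecting at 5 or more responders has size 0.0948, which is above 0.0900.

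A reader who takes 0.09 as a bound and derives the cutoff at 35 participants would arrive at 6 or more responders, with size 0.0330 and power 81.3%. On that reading the level, the cutoff and the 91% power could not all be right. The plan also introduces the cutoff as a consequence of the sentence before it, which can suggest that it was derived from the level.

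What would be at stake is the stated false-positive rate of the trial's only efficacy decision rule. There could also be an awkward report if exactly 5 of 35 respond: the rule rejects, while the exact p-value of 0.0948 lies above a literal 0.0900.

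**Working it through.** **Inputs**, all from Section 14.2 (the sample size also from Section 14.3): n = 35, null rate 0.07, target rate 0.22, reject if X ≥ 5, one-sided exact binomial test. All 35 participants are in the denominator.

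**Formula.** P(X ≥ 5) = 1 − Σ C(35, k) p^k (1 − p)^(35−k), summed over k = 0 to 4.

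**Step 1: reproduce the power (p = 0.22).** The terms for k = 0 to 4 are 0.00017, 0.00165, 0.00792, 0.02456 and 0.05541, which sum to 0.08971. Power = 1 − 0.08971 = 0.9103. The plan's 91% is reproduced.

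**Step 2: type I error (p = 0.07).** The terms are 0.07887, 0.20777, 0.26586, 0.22012 and 0.13254, which sum to 0.90516. Size = 1 − 0.90516 = 0.0948. To two decimals this is 0.09, the figure in the plan.

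**Step 3: neighbouring cutoffs at n = 35.**

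| Reject if | Size at 0.07 | Power at 0.22 |
|---|---|---|
| ≥ 4 | 0.2274 | 0.9657 |
| ≥ 5 | 0.0948 | 0.9103 |
| ≥ 6 | 0.0330 | 0.8134 |

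Only the middle row gives 91% power, and only the middle row has a size that prints as 0.09. The printed cutoff, power and 0.09 therefore all describe the same rule. Had 0.09 been applied as a ceiling, the plan would show 6 or more responders and 81% power. It shows neither.

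**Step 4: compare the gap with the precision of the inputs.** The excess over a literal 0.09 is 0.0948 − 0.0900 = 0.0048. The null rate is a weighted average over 11 cohorts, printed to two decimals. The size of the ≥ 5 rule across values that print as 0.07 is:

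| Null rate | Size |
|---|---|
| 0.0650 | 0.0741 |
| 0.0689 | 0.0900 |
| 0.0700 | 0.0948 |
| 0.0749 | 0.1178 |

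The range is 0.1178 − 0.0741 = 0.0437, about nine times the gap (0.0437 / 0.0048 = 9.1).

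**Step 5: look for a consequence.** The rule is a count, so the decision at any number of responders is fixed without reference to 0.09, and no section plans to compare a p-value with 0.09. The one outcome where the label could be noticed is exactly 5 of 35, with probability 0.0948 − 0.0330 = 0.0618 (0.0619 before rounding) under 0.07 and 0.9103 − 0.8134 = 0.0969 under 0.22. There the p-value of 0.0948, reported to the plan's two decimals, is again 0.09.

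**The case for a change.** The strongest case for the concern is about the word. The plan does not call 0.09 an approximate type I error; it attaches it to the test as its level, and a level is by definition not exceeded. Other routes to the figure do not rescue a literal reading. With 34 in the denominator the size is 0.0860, but the power falls to 89.6%. A continuity-corrected normal approximation gives 0.0872, but the plan names an exact test. The test should also be judged at the null rate as stated, 0.07, where the size is 0.0948.

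These calculations are right, and a third decimal would have been more exact. But the objection depends wholly on reading 0.09 as a bound fixed in advance, and no section says that it is. It is also an unusual figure to choose beforehand and an ordinary one to report as the rounded size of a chosen cutoff. Describing a discrete test by its rounded attained size is loose wording, not wrong arithmetic.

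Section 14.4.2 raises a different question. It says "All conclusions should be based on all evaluable participants", while "Participants in response categories 5-9 will not be considered evaluable but will remain within the intention to treat analysis". Which participants form the denominator matters for the operating characteristics, but it has no bearing on whether 0.09 is the correct rounding at 35. Writing a denominator of all 35 into Section 14.2 to tidy the label would conflict with the first of those statements unless Section 14.4.2 were changed too.

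**Conclusion.** The concern does not hold. At 35 participants and 5 or more responders, the exact size is 0.0948 and the exact power 0.9103. The plan's 0.09 and 91% are both correct at the precision it uses, and they agree with the sample size and the cutoff. The apparent contradiction arises only if 0.09 is taken as a strict pre-set ceiling, which the plan does not state. The difference of 0.0048 is well inside the uncertainty from printing the null rate to two decimals, and it alters no cutoff, sample size, power figure or decision.

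The conclusion assumes that 0.09 is the rounded attained size of the stated rule, that the null rate is taken at its printed value of 0.07, and that all 35 planned participants are counted. It leaves open how evaluable and intention-to-treat participants are to be handled under Section 14.4.2.
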